1- Initiation of randomized treatment at Visit 2 can only begin if the patient meets the criteria for Initiation of Treatment. Please refer to Sections [3.3.2](#) and [3.3.3](#).

2- At Visit 10, Non- Responders (NR) will receive their last study drug administration and Responders (R) will have their End of Study (EoS) visit.

3- Should a patient prematurely discontinue before their scheduled EoS every effort should be made to keep the patient in the trial and complete all of the remaining study visits or at a minimum an early EoS visit. Patients who prematurely discontinue before V7/Wk16 are considered Non-Responders.

4- C = Complete Physical Examination (PE) includes general appearance as well as evaluation of all organ systems; T = Targeted physical examination includes evaluation of organ systems associated with AE(s) symptoms or laboratory abnormalities. At Visit 10 complete physical examination will be performed for Responders (EOS), targeted physical examination will be performed for Non-Responders. Please refer to Section [5.2.1](#).

5- Vital signs will be assessed at predose, at approximately 5 minutes after the end of infusion, and 60 mins after the end of infusion at visits with i.v. administration.

6- Safety laboratory tests include clinical chemistry, haematology, coagulation, and urinalysis, and will be performed centrally. Local Labs may be used for dosing decisions prior to i.v. administration. Please refer to Section [5.2.3](#).

7- Only applicable for women of childbearing potential. S – serum pregnancy test (performed at screening). U – urine pregnancy tests will be performed at all other visits indicated in the [Flow chart](#). Urine pregnancy testing should be done prior to administration of study drug. Study drug should only be administered in case of a negative test result. (S) - in case of a positive urine pregnancy test, a serum pregnancy test will be done. Please refer to Section [5.2.5.2](#).

8- ECG measurements should always precede blood sampling and drug administration. Clinically significant abnormal findings should be reported as AEs in the eCRF.

9- Infection testing includes tuberculosis, hepatitis B, hepatitis C, and HIV assessments. Please refer to Table [5.2.3: 1](#). For the EoS visit only tuberculosis and hepatitis B testing will be performed. For Responders the Infection testing will be conducted at V10 (Week28) which corresponds to their EoS. For Non Responders the Infection testing will be conducted at V11.

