3.1 OVERALL TRIAL DESIGN AND PLAN

This is a double-blind, placebo-controlled study assessing the safety, tolerability and efficacy of 600 mg BI 655130 compared to placebo given intravenously every 4 weeks in patients with moderate to severe atopic dermatitis. Safety and tolerability will be evaluated based on AE data collected and physical examination at every visit. At W16 patients will be evaluated for response to treatment by the change in EASI score compared to baseline. Patients who have responded, defined as having attained at least 75% reduction in EASI score compared to baseline will no longer receive treatment and will be followed at W 20, 24 and 28 to evaluate the sustainability of their response. If this patient reaches a 50% reduction in EASI score compared to baseline prior to the planned EOS at Week 28, they will immediately perform EOS and will be given the opportunity to receive treatment in an open label extension trial.

Patients who have not responded, defined as attained less than 75% reduction in EASI score compared to baseline will receive 600 mg BI 655130 at W16, 20, 24 and 28. Patients re-allocated to treatment, who reach EOS will be offered participation in the extension trial if they meet the eligibility criteria.

After re-allocation at Week 16, a patient will know what treatment they are on but will remain blinded to the treatment received until Week 16.

Figure 3.1.1 Trial design

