3.2 DISCUSSION OF TRIAL DESIGN, INCLUDING THE CHOICE OF CONTROL GROUP(S)

The placebo control is required to control for investigator bias and/or beneficial effects of being in a clinical trial. The 2:1 randomization (active: placebo) is warranted in order to maximize the number of patients receiving active treatment and is being controlled for from a statistical standpoint. The rationale for switching responding patients to follow-up with no-treatment at Week 16 is to evaluate the duration of clinical response off treatment. In addition, patients who have not attained at least a 75% reduction in EASI score compared to baseline will have the opportunity to receive (or continue) active treatment.

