6. GENERAL ANALYSIS DEFINITIONS

6.1 TREATMENTS

For basic study information on the treatment to be administered, assignment to treatment, and selection of dose, cf. Section 4 of the CTP.

In the blinded treatment phase, all patients will receive either intravenous doses of 600mg of BI 655130 solution for infusion (at weeks 0, 4, 8, and 12), or Placebo.

At Week 16, all patients will be evaluated with the EASI Score. Non-responders (EASI < 75) will be re-allocated to receive BI open label trial drug from Week 16 through Week 28; they will be followed until Week 44. Responders (EASI >= 75) will be re-assigned to receive no further trial treatment but will be expected to come to all visits up to Week 28, when EOS visit is planned.

The following trial periods/phases are defined:

Table 6.1: Flow chart of trial period/phases

Trial phase	Description	Start (included)	End (excluded)
Screening phase	Screening	Date of informed consent	Date of start of first infusion of study drug (day 1).
Blinded Treatment phase	Randomised On-treatment period	Date of start of infusion of first study drug (Day 1)	Week 16 visit date + 1 day
Open label Treatment phase ¹	Re-allocation period (Either open label BI655130 or No treatment)	Week 16 visit date + 1 day	Date of EoS Participation visit + 1 day

Dates are defined individually per patient. If more than one date is associated with a specific visit, measurements associated with a specific date are assigned to a study analysis phase according to the rules specified in the table. An analysis phase will not extend beyond the start date of the following phase.

¹ Non-responders (i.e. EASI<75) at Week 16 will be re-allocated to BI655130 600mg IV open label and will continue in the trial until Week 44. Responders (EASI>=75) at Week 16 will be re-allocated to no treatment and will be observed until Week 28 or the day when they return to a 50% reduction in EASI score (EASI50) and start the treatment in the extension trial.

Patients who discontinue the treatment but will continue on trial visits will be included in analyses with the available data. For patients who discontinue trial prematurely only available data will be used in the analyses.

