 - **"Speso 600 mg IV q4w"** (i.e., patients randomised to BI 655130 in the double-blind treatment period and who did not receive an open-label BI 655130 treatment starting from Week 16 (V7))
 - **"Total"** (i.e., patients randomised either to Placebo or BI 655130 in the double-blind treatment period and who did not receive an open-label BI 655130 treatment starting from Week 16 (V7))
- **"Open-label treatment: Speso 600 mg IV q4w"**
 - **"Placebo"** (i.e., patients randomised to Placebo in the double-blind treatment period and received an open-label BI 655130 treatment starting from Week 16 (V7))
 - **"Speso 600 mg IV q4w"** (i.e., patients randomised to BI 655130 in the double-blind treatment period and received an open-label BI 655130 treatment starting from Week 16 (V7))
 - **"Total"** (i.e., patients randomised either to Placebo or BI 655130 in the double-blind treatment period and received an open-label BI 655130 treatment starting from Week 16 (V7))

Treatment groups for the safety analysis for the whole trial will be labelled as follows:

- **"Speso 600 mg IV q4w"** (i.e., patients randomised to BI 655130 600 mg)
- **"Placebo"** (i.e., patients randomised to Placebo)
- **"Total Speso 600 mg IV q4w OL"** (i.e., patients randomised either to Placebo or BI 655130 600mg and assigned to BI 655130 600 mg open-label treatment at Week 16)

More details on the technical implementation of these analyses are provided in the ADS Plan of this TSAP.

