6.6.2 Efficacy data

Binary efficacy endpoints

The primary imputation approach for binary endpoints will be No Response Imputation (NRI) described below.

1. If a patient prematurely discontinues study medication administration for any reason, then all data subsequent to the discontinuation will be considered to be missing. The cut-off date to be used is the last dose of study medication administration + 4 weeks (including the extended time windows).
2. For endpoints which are measured at multiple visits, if there are data at visits both before and after the visit with a missing outcome, then impute as success (a responder) only if both neighbouring visits also represent a success (independent of whether the preceding and following observations were selected for analysis based on time windows described in [Section 6.7](#)).

For all patients with a missing visit outcome, impute as a failure to achieve a response (non-responder).

In addition, for all binary endpoints (i.e. endpoints that are either 1 (patient responded) or 0 (patient did not respond)), frequency tables with observed data will be presented.

Categorical efficacy endpoints with more than two outcomes

Some endpoints or their subscores are categorical with more than two potential outcomes (e.g. IGA, DLQI). As a general rule, imputation will only be applied on the complete score. In case if a categorical subscore is analysed separately, no imputation will be applied (only observed data will be analysed).

Continuous efficacy endpoints

For efficacy endpoints which are continuous in nature, the use of a restricted maximum likelihood (REML)-based mixed model repeated measures (MMRM) approach, if applicable, will ensure that missing data are handled implicitly, via a missing at random assumption, by the statistical model.

[figure not shown]

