Tabulations of frequencies for categorical data will include all possible categories and will display the number of observations in a category as well as the percentage (%) relative to the respective treatment. Percentages will be rounded to one decimal place. The category missing will be displayed if and only if there actually are missing values. Percentages will be based on all patients in the respective patient set whether they have non-missing values or not.

Disposition of the patient population participating in the trial will be summarised by presentation of the frequency of patients screened, entered/randomised, screened but not entered, treated, entered but not treated, who completed all doses of trial medication as planned (overall, in the double-blind treatment period, and in the BI open-label treatment period), who prematurely discontinued study drug administration by reason (overall, in the double-blind treatment period, and in the BI open-label treatment period), patients still ongoing in the study, those, who completed the observational period as planned, who prematurely discontinued study participation, who completed Week 4 visit (V4), who completed the re-allocation visit at Week 16 (V7), number of patients reallocated to BI open-label treatment. Disposition will be listed by country.

The frequency of patients with iPDs will be presented for the RS by treatment. The IPDs will be listed per patient indicating whether or not the iPD led to exclusion from patient sets analysed.

The frequency of patients in each of the different analysis sets will also be presented by treatment.

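### The post-Week-16 No Treatment efficacy groups carry no EASI75 condition, so read literally they mix responders with other patients who took no open-label drug

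*SAP*

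**What the plan says.** **The group.** SAP 6.1 lists the labels for the efficacy analysis after Week 16. Under the *No Treatment* heading, the active-arm group is "patients randomised to BI 655130 in the double-blind treatment period and who did not receive an open-label BI 655130 treatment starting from Week 16". The Placebo and Total groups follow the same pattern. Response at Week 16 is not part of any of the three definitions.

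**The design.** Protocol 3.1 says that patients with at least a 75% EASI reduction "will no longer receive treatment and will be followed at W 20, 24 and 28 to evaluate the sustainability of their response". Protocol 3.2 gives the reason for taking them off drug: "to evaluate the duration of clinical response off treatment". SAP 6.1 repeats the rule: "Responders (EASI >= 75) will be re-assigned to receive no further trial treatment". SAP Table 6.1: 2, on adverse events, pairs no treatment with Responder only and has no row for a Non-Responder without open-label drug.

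**Early stoppers.** Footnote 3 of the protocol Flow Chart states: "Patients who prematurely discontinue before V7/Wk16 are considered Non-Responders". The same footnote asks sites to keep such patients in the trial and at visits. The full analysis set (SAP 6.3) needs only one dose and a baseline EASI, so they stay in it.

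**Data handling.** For binary endpoints, SAP 6.6.2 sets data beyond four weeks after the last dose to missing in patients who stop early. It then says: "For all patients with a missing visit outcome, impute as a failure to achieve a response (non-responder". Tables of observed data are planned as well. SAP 7 adds: "Percentages will be based on all patients in the respective patient set whether they have non-missing values or not". SAP 6.1, however, says that patients who are off drug but still attending are analysed with the data they have, and that "For patients who discontinue trial prematurely only available data will be used in the analyses". SAP 6.7 bases imputation, where it applies, on observations from the on-treatment period.

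**The concern.** The off-drug follow-up asks one question: how long does an EASI75 response last once treatment stops? Only patients who had that response can answer it. The SAP label selects instead on not having received open-label drug, which is a different condition. A patient who stopped early because of an adverse event and kept attending meets the label. So does a Week 16 non-responder who declined open-label drug. Neither had the response whose duration is being described.

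The trial plans about 45 patients, so the responder group will be small and two or three misplaced patients can change what a table shows. A reader of the report would take the *No Treatment* columns as the course of responders off drug, and that may not be what they contain.

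**Working it through.** **1. Inputs.** The documents give no EASI75 rate, early-stopping rate or sustained-response rate for this trial, so there is no plan figure to reproduce. The only planned quantity used is 30 active patients (Protocol synopsis). The sample-size calculation has no bearing on this point.

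**2. Membership, label against design.**

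| Patient | Meets the SAP 6.1 label? | Meant to be on no treatment? |
|---|---|---|
| EASI75 at Week 16, re-assigned to no treatment | Yes | Yes |
| Week 16 non-responder who receives open-label drug | No | No |
| Stopped drug before Week 16, still attends, no open-label drug | Yes | No |
| Week 16 non-responder who takes no open-label drug | Yes | No |
| Left the trial before Week 16 | By the words, yes; but no Week 16 visit date to start the phase (Table 6.1: 1) and no later data | No |

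Rows 3 and 4 are the mismatch. Row 5 is doubtful.

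**3. Effect on a displayed rate.** Let R be the responders in the group, S the other patients in it, m the share of responders still in response at a visit, and q the share of the others counted as in response. Then

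displayed rate = (m × R + q × S) / (R + S).

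With the group limited to responders, the rate is m. As labelled, it is below m whenever S is at least 1 and q is below m. If every one of the S patients is imputed as a failure, q = 0 and the rate is m × R/(R+S).

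Multiplier R/(R+S), assuming R of 6 to 15 (20% to 50% of 30) and S of 1 to 6:

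| | S = 1 | S = 3 | S = 6 |
|---|---|---|---|
| R = 6 | 0.86 | 0.67 | 0.50 |
| R = 9 | 0.90 | 0.75 | 0.60 |
| R = 12 | 0.92 | 0.80 | 0.67 |
| R = 15 | 0.94 | 0.83 | 0.71 |

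The share of the group who are not responders is 1 minus the entry: 6% to 50%. Example: R = 9 with 6 still in response gives 6/9 = 67%. With S = 3, all imputed as failures, the table shows 6/12 = 50%. With S = 6 it shows 6/15 = 40%. With S = 0 it stays at 67%.

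**4. Does the imputation reach beyond Week 16?**

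- *For:* SAP 6.6.2 sets no last visit, and the denominator rule in SAP 7 is general.
- *Against:* every binary efficacy endpoint visible in SAP 5.2.2 and 7.5.2.1 is at Week 4 or 16. SAP 6.1 speaks of available data. SAP 6.7 ties imputation to the on-treatment period, a term that Table 6.1: 1 attaches to the blinded phase only.

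The text does not settle it. With available data only, patients who attend still enter the summaries, but with their observed values. A mean is then a weighted average of the two kinds of patient, and its direction of error depends on how the S patients fare.

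**The case against.** The intended population is clear from the rest of the SAP. The prose of 6.1 and Table 6.1: 2 send only responders to no treatment. The disputed text is a list of labels, and technical detail is deferred to an ADS Plan that is not public. Redacted endpoint and analysis sections may also restrict the group. All of this stands as to intent, and a restriction elsewhere cannot be excluded. But none is visible, and someone programming from the label as written would include the other patients.

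Three stronger readings are tempting, and the documents do not support them.

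- A reader might infer that early stoppers are counted as failures and that durability is therefore understated by a definite amount. That needs the imputation rule to apply after Week 16, which SAP 6.1 and 6.7 put in doubt. It also needs rates that the documents do not give.
- A reader might add everyone who left before Week 16 to the denominator. Those patients have no start date for the phase and no data in it, so they matter only under the same disputed reading.
- A reader might call these tables the only durability readout. With sections redacted, that cannot be known.

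The early exit of responders who fall back to a 50% reduction is a separate question, which redefining the group neither causes nor cures.

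It is also fair that the stakes are limited. SAP 6.1 makes the post-Week-16 results descriptive, SAP 7 calls all efficacy analyses exploratory, and individual values will be listed.

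**Conclusion.** The point holds as a mismatch between a stated group definition and the purpose of the follow-up. Read literally, the *No Treatment* groups are not the Week 16 EASI75 responders whom the design takes off drug, and their summaries need not describe those responders.

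The size cannot be fixed from the documents. For the active arm, under the assumed R and S, 6% to 50% of the group would not be responders. Only if imputed failure and the all-patients denominator carry past Week 16 does this become a multiplier of 0.94 to 0.50 on the sustained-response rate. If no patient outside the responder group goes without open-label drug, S is 0 and nothing changes. The primary comparison at Week 16 is unaffected. The correction is worth making because the rule is stated, the mismatch is plain, and the repair is nearly free.

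**What to change.** In SAP 6.1, define the three *No Treatment* efficacy groups (Placebo, active, Total) as patients with EASI75 at Week 16 who were re-allocated to no treatment. Show all other patients without open-label drug in a separate display.

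Say where a patient belongs who stopped drug before Week 16 but has an observed 75% reduction at that visit. Flow Chart footnote 3 makes this patient a Non-Responder, while SAP 5 classes by the Week 16 score alone.

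Reconcile SAP 6.1, 6.6.2 and 6.7 in one sentence stating whether non-responder imputation applies to visits after Week 16, and with which denominator.

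The cost is one group flag and one extra descriptive display. Protocol 4.1.3 has the re-assignment made through the IRT, and deviation F2.03 in SAP Table 6.2: 1 already checks it. Trial conduct does not change.

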2. TRIAL OBJECTIVES AND ENDPOINTS

2.1 MAIN OBJECTIVES, PRIMARY AND SECONDARY ENDPOINTS

2.1.1 Main objectives

The primary objective of this trial is to investigate the safety, tolerability and efficacy of BI 655130 in patients with AD following multiple intravenous administrations of 600 mg compared to placebo.

While the main objective is to assess safety and tolerability of BI55130 in patients with AD, these endpoints can only be analyzed descriptively. Thus, the endpoints to be discussed below will focus on efficacy endpoints that are more amenable to other statistical analyses and where sample size considerations may be more relevant.

A description of the endpoints to be determined, and the observations along with specific information as how to collect the data for that information, is provided in Section [5](#).

[figure not shown]

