7.3.4 Safety analyses

Adverse events will be coded using the Medical Dictionary for Drug Regulatory Activities (MedDRA). Standard BI summary tables and listings will be produced. All adverse events with an onset between start of treatment and end of the residual effect period (REP), a period of 16 weeks after the last dose of trial medication, will be assigned to the on-treatment period for evaluation.

All treated patients will be included in the safety analysis. In general, safety analyses will be descriptive in nature and will be based on BI standards. No hypothesis testing is planned.

Statistical analysis and reporting of adverse events will concentrate on treatment-emergent adverse events, i.e. all adverse events occurring between start of treatment and end of the REP. Adverse events that start before first drug intake and deteriorate under treatment will also be considered as 'treatment-emergent'.

[figure not shown]
Frequency, severity, and causal relationship of adverse events will be tabulated by system organ class and preferred term after coding according to the current version of the Medical Dictionary for Drug Regulatory Activities (MedDRA) at database lock.

[figure not shown]
Laboratory data will be analysed both quantitatively as well as qualitatively. The latter will be done via comparison of laboratory data to their reference ranges. Values outside the reference range as well as values defined as clinically relevant will be summarised. Treatment groups will be compared descriptively with regard to distribution parameters as well as with regard to frequency and percentage of patients with abnormal values or clinically relevant abnormal values.

Vital signs, physical examinations, or other safety-relevant data observed at screening, baseline, during the course of the trial and at the end-of-trial evaluation will be assessed with regard to possible changes compared to findings before start of treatment.

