For the final analysis of the trial to be performed once all patients have completed through the planned period, results will be summarized including the data from the reallocation period (Open-label Treatment phase). Results will be presented separately and in descriptive manner. The time windows for data presentation in this analysis are described in [Table 6.7: 1](#). In addition, analyses including the data from the double-blind period (initially used for the Primary Analysis) will be re-run after the final database lock.

To distinguish between assignment to trial periods/phases and AE assignments, please, refer to [Table 6.1:2](#).

Table 6.1: 2 AE assignment to analysis treatment groups

Randomised treatment	EASI75 response at Week 16	Open-label period	AE assignment to analysis treatment group
PLACEBO	Responder	No Treatment	AE that occurred between first randomised study drug intake and min[(EoS visit date), (last randomised study drug administration date + 112 days)] will be analysed under PLACEBO. AEs occurring later will be listed only.
PLACEBO	Non-Responder	BI 655130 Treatment	AE that occurred between first randomised study drug intake and Week 16 visit date (excluding) will be analysed under PLACEBO. AEs occurring later will be analysed under Open-label BI Treatment.
BI 655130	Responder	No Treatment	AE that occurred between first randomised study drug intake and min[(EoS visit date), (last randomised study drug administration date + 112 days)] will be analysed under BI 655130. AEs occurring later will be listed only.
BI 655130	Non-Responder	BI 655130 Treatment	AE that occurred between first randomised study drug intake and Week 16 visit date (excluding) will be analysed under BI 655130. AEs occurring later will be analysed under Open-label BI Treatment.

Treatment groups up to Week 16 will be labelled as follows:

- **"Speso 600 mg IV q4w"** (i.e., patients randomised to BI 655130 600 mg)
- **"Placebo"** (i.e., patients randomised to Placebo)
- **"Overall Total"** (across treatments: Placebo and BI 655130 600 mg), where appropriate.

Treatment groups for the efficacy analysis after week 16 will be labelled as follows:

- **"Open-label treatment: No Treatment"**
 - **"Placebo"** (i.e., patients randomised to Placebo in the double-blind treatment period and who did not receive an open-label BI 655130 treatment starting from Week 16 (V7))

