6.3 SUBJECT SETS ANALYSED

The following analysis sets will be defined for this trial:

- Enrolled set (ES)
This patient set includes all patients who signed informed consent. It will be used for display of patient disposition.
- Randomized set (RS)
This patient set includes all patients who were randomized into the trial. It will be used for display of patient disposition, baseline and demographic characteristics, and patients with IPDs.
- Safety analysis set (SAF)
This patient set includes all randomized patients who received at least one dose of study drug. It will be the main analysis set for presentation of safety. Treatment assignment will be based on the actual treatment administered. Actual treatment refers to the actual treatment administered at the first dosing. This treatment should be followed through the whole trial, regardless of the initially randomised treatment.

- Safety analysis set in the open-label treatment period (SAF-OL)
This patient set includes all randomized patients who received at least one dose of study drug and received study medication after re-allocation visit (i.e., after Week 16 visit). Treatment assignment will be based on the actual treatment administered starting from Week 16 visit. This analysis set will be the main set for presentation of the safety data for the treatment re-allocation period.
- Full analysis set (FAS)
This patient set includes all patients in the SAF who had a baseline measurement for the primary endpoint. It will be the main analysis set for presentation of efficacy results. Treatment assignment will be as randomized.
- Full analysis set including completers (FAS-C)
This analysis set includes all patients in the FAS who completed double-blind treatment, i.e., did not prematurely discontinue treatment up to (and including) Week 12.
- Pharmacokinetic parameter set (PKS)
This patient set includes all patients in the SAF who provide at least one evaluable observation for the BI 655130 concentration, which was not flagged for exclusion. This patient set will be used for the display of concentrations.

The discussion of all exceptional cases and problems and the decisions on the allocation of patients to populations will be made at latest at the DBLM.

Handling of Treatment Misallocations in Analysis Sets

If a patient was administered incorrect treatment during the study, then for safety the following will be used in addition:

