7.8.1 Adverse events

AEs will be coded with the most recent version of MedDRA.

The analyses of AEs will be descriptive in nature. All analyses of AEs will be based on the number of patients with AEs and not on the number of AEs. System organ classes (if applicable) will be sorted according to the standard sort order specified by the EMA, preferred terms (if applicable) will be sorted by total frequency (within system organ class) across all treatment arms.

The analyses of AEs will be performed for double-blind period and for the re-allocation period separately.

For further details on summarization of AE data, please refer to “Analysis and Presentation of Adverse Event data from Clinical Trials” [BI-KMED-BDS-HTG-0066] (7) and “Handling of missing and incomplete AE dates” [BI-KMED-BDS-HTG-0035] (4).

The analysis of AEs will be based on the concept of treatment emergent AEs. If only the start date of an AE is collected (without start time), any AE occurrence on the same day as the first BI 655130 administration will be assigned to the on-treatment phase.

An overall summary of AEs will be presented by treatment.

This overall summary will include summary statistics for the class of other significant AEs (sponsor definition based on ICH E3 (9)) and for the class of AESIs.

The following is considered an AESI in this trial:

- Hepatic injury
- Infusion reactions including anaphylactic reaction
- Severe infections
- Opportunistic and mycobacterium tuberculosis infections

The investigator has to classify on the eCRF whether an observed AE was an AESI or not. Only those AEs that are indicated by the investigator as AESI in the eCRF will be analysed in this category.

Based on the specification provided in ICH E3 (9), the sponsor has defined AEs which are to be classified as ‘other significant’. These will include those non-serious AEs which were reported with ‘action taken = Drug withdrawn’ or ‘action taken = Dose reduced’.

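### Open-label safety after Week 16 is summarised in one column that pools first BI 655130 exposure in ex-placebo patients with continued exposure in ex-BI patients

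*SAP*

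**What the plan says.** Protocol 3.1 sends non-responders of both arms to open-label drug at Week 16: they are "defined as attained less than 75% reduction in EASI score compared to baseline will receive 600 mg BI 655130 at W16, 20, 24 and 28". Responders stop treatment.

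SAP 6.1 lists three groups for whole-trial safety: patients randomised to BI 655130, patients randomised to placebo, and *Total Speso 600 mg IV q4w OL*, which is "patients randomised either to Placebo or BI 655130 600mg and assigned to BI 655130 600 mg open-label treatment at Week 16". Table 6.1: 2 closes the blinded groups for non-responders just before the Week 16 visit date. From then on it gives the same instruction for both randomised arms: "AEs occurring later will be analysed under Open-label BI Treatment".

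SAP 6.3 defines the open-label safety set, SAF-OL, and states: "Treatment assignment will be based on the actual treatment administered starting from Week 16 visit". SAP 7.8.1 adds: "The analyses of AEs will be performed for double-blind period and for the re-allocation period separately". SAP 7.8.2 and 7.8.3 make the same split by period for laboratory data and vital signs. None of these sections adds a split by earlier treatment.

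For efficacy after Week 16, SAP 6.1 does split patients on open-label drug by randomised arm, into Placebo, Speso and Total.

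**The concern.** Protocol 2.1.1 puts safety first: "While the main objective is to assess safety and tolerability of BI55130 in patients with AD". The re-allocation at Week 16 gives the trial a second set of patients meeting the drug for the first time, which is useful when the active arm has only 30 patients. Their experience is not exchangeable with that of patients who have already had up to four infusions. Infusion reactions are an AESI and anti-drug antibodies are a listed safety assessment, and either may depend on how many infusions a patient has had.

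Under Table 6.1: 2, a reaction to an ex-placebo patient's first BI 655130 infusion, given at the Week 16 visit, is counted in the open-label column. There it shares a denominator with patients on their fifth infusion. The SAP gives no reason for keeping randomised origin in the efficacy tables and dropping it from the safety tables.

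**Working it through.** **Inputs from the documents.** 30 active and 15 placebo patients (Protocol synopsis). Blinded doses at Weeks 0, 4, 8 and 12 (SAP 6.1). Open-label doses at Weeks 16, 20, 24 and 28 (Protocol 3.1). Half-life about 4 weeks (Protocol 1.2.3). Residual effect period: "a period of 16 weeks after the last dose of trial medication" (Protocol 7.3.4).

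**Arm sizes.** The plan's sample size reproduces. With delta 25, SD 30, two-sided alpha 0.10, power 80% and 2:1 allocation:

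placebo n = (1 + 1/2) × (1.645 + 0.842)² × (30/25)² = 1.5 × 6.18 × 1.44 = 13.4, rounded up to 14.

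That gives 28 + 14 = 42, as in Protocol 7.7. The plan enters about 45. No figure in the plan is disputed here.

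**Infusion numbers.** Four open-label doses are infusions 1–4 of BI 655130 for ex-placebo patients. For ex-BI patients who had all four blinded doses they are infusions 5–8.

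**Drug on board at Week 16.** Taking simple exponential decline with a 4-week half-life, the four blinded doses leave 1/2 + 1/4 + 1/8 + 1/16 = 15/16 of one dose. The residual effect period of the Week 12 dose ends at Week 12 + 16 = Week 28, so it overlaps the open-label dosing.

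**Length of the mixed window.** Last open-label dose at Week 28, plus 16 weeks, is Week 44. The column can hold events from the Week 16 visit to as late as Week 44.

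**Composition of the column.** The documents give no Week 16 EASI75 rates. Assume 0–30% on placebo and 0–50% on active, with no dropout.

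- Ex-placebo patients dosed: 15 × (1 − 0.30) = 10.5 to 15 × (1 − 0) = 15.
- Ex-BI patients dosed: 30 × (1 − 0.50) = 15 to 30 × (1 − 0) = 30.
- Lowest ex-placebo share: 10.5 / (10.5 + 30) = 26%.
- Highest ex-placebo share: 15 / (15 + 15) = 50%.

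**Effect on a reported rate.** Let w be the ex-placebo share, p1 the event rate on first exposure and p2 the rate on continued exposure. The pooled rate is w·p1 + (1 − w)·p2, so pooled rate − p2 = w·(p1 − p2). With w between 0.26 and 0.50, the table shows 26–50% of the true excess, whatever p1 and p2 are.

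**What a separate column can show.** With no events in n patients, the 95% upper bound is 1 − 0.05^(1/n): 25.9% for n = 10 and 18.1% for n = 15.

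**What first-exposure patients add in total.** The chance of seeing at least one case of a 5% event is 1 − 0.95^n. It is 78.5% for n = 30 (active arm alone), 87.1% for n = 40 and 90.1% for n = 45 (active plus ex-placebo).

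**The case against.** The strongest reply is that the main evidence on first exposure is intact. Table 6.1: 2 stops blinded AE assignment for non-responders at the Week 16 visit. SAP 7.8 adds AE tables to Week 16 without the residual period, and SAP 7.8.1 to 7.8.3 report the double-blind period separately. Thirty first-exposure patients are thus read against 15 concurrent placebo patients with no pooling. This stands. A reader might infer that the pooled column contaminates the blinded comparison; it does not.

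A reader might also infer that ex-placebo events cannot be recovered. SAP 7 lists individual values for all patients, and only about 10 to 15 patients are involved, so the gap is in the summary tables.

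Two further inferences go beyond the text. One is that the ex-BI patients were selected for tolerating the drug. Re-allocation is by EASI response, and tolerance is at most implied by still being dosed at Week 16. The other is that a particular reaction rate is being hidden. The documents give no rates by infusion number in this population, and the one potential infusion reaction in the multiple-dose volunteer trial with a stated infusion number was at the third.

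The SAP refers technical detail to an ADS Plan that is not among the documents, and parts of the SAP are redacted, so a split could exist there. The SAF-OL rule does not itself forbid sub-columns. For anti-drug antibodies, SAP 7.8.5.2 promises results by treatment and visit without saying which treatment columns apply. None of this supplies the missing table: the safety columns are set in SAP 6.1, and they pool.

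**Conclusion.** The point holds as a gap in the planned summary tables. Followed as written, SAP 6.1 and Table 6.1: 2 mix first and continued exposure in the only open-label safety column. The ex-placebo share of roughly a quarter to a half rests on the assumed response rates and on no dropout; the infusion numbering rests on all blinded doses having been given. The gain from splitting is modest, because the separate ex-placebo column would be small and uncontrolled. It is still worth having, since safety is the stated main objective and the analysis is descriptive, so a split costs no power. The documents do not support any claim that the trial's safety conclusions up to Week 16 are at risk.

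**What to change.** In SAP 6.1, replace the single open-label safety column with the layout already used for efficacy: Placebo to Speso OL, Speso to Speso OL, and Total Speso OL. Apply it to AEs, drug-related AEs, AESIs including infusion reactions, and anti-drug antibodies. State in Table 6.1: 2 that open-label AEs keep the randomised arm as a sub-group.

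In the same edit, reconcile two passages on SAF-OL. SAP 7.8 bases safety beyond Week 16 on SAF-OL for patients who are not receiving open-label BI 655130. SAP 6.3 defines that set as patients who did receive study medication after re-allocation.

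A combined summary of the first 16 weeks on BI 655130 (the active arm from Day 1, plus ex-placebo patients from their first open-label infusion) is optional. If produced, it should be labelled as mixing blinded and open-label observation.

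The cost is SAP wording and extra table columns with small counts. No new data are needed.
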